Exclusion Criteria. Patients with left ventricular assistive devices, documented chronic pain, use of home infusion pain pumps, or documented active addictive behaviors (documentation of current substance use or current hospitalization for substance use in medical record) will be excluded from this study because of the unique needs of their FCGs are not addressed by this study.

Recruitment. Eligible FCGs and care recipients will be introduced to the study by a trained SC over the phone or in person using an approved detailed phone script. Due to COVID-19 hospital visitation restrictions, we will not rely on members of the hospital palliative care consulting team to introduce the study with potential caregiver participants during consultations with the care recipient. A study coordinator may meet with the palliative care teams as needed or call palliative care team members to ascertain potential recruits.

Our target population is community-dwelling adult FCGs providing care to a loved one who has a serious life-limiting condition and receives a palliative care consult. However, we will also consent the care recipient. Informed consent of the hospitalized care recipient will be obtained by a trained SC in person via written informed consent or via Ptrax Docu Sign, over the phone (verbally) or email of electronic consent following a conversation outlining the risks, benefits and goals of the investigation. The SC will allow ample time for this conversation, which will include the care recipient's understanding that the study involves collection of data from their electronic health record, discussion of their symptoms with their FCG, and collaboration between their FCG and their primary care provider/specialty providers related to goals of care.

Enrollment. The study coordinator will either visit in person or call the FCGs and care recipients prior to the care recipients being discharged, to further explain the study, obtain written consent in person and/or via Ptrax DocuSign or email electronic consent and, if possible, collect baseline data.

If a care recipient lacks the cognitive capacity to provide consent based on an IRB-approved assessment of their understanding of the study, the care recipients' documented legal authorized representative will sign or verbally the consent (see above) form on their behalf. We will then document assent of the care recipient on a separate assent form.

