Upon completion of the informed consent process, the SC will retain documentation of the FCG's consent and the care recipient's consent/assent along with the assessment in the research study files, including the name and job title of the study team member who explained the study, a brief description of what was explained, questions (if any) that were asked and answered, confirmation that the subject expressed understanding of the study and willingness to participate, and the list of written information given to the subject.

Based on recruitment approaches, including introduction of the study by our trained SC and, when possible, by the members of the hospital palliative care consulting service, review of palliative care admission lists by a study coordinator, FCG remuneration, our prior experience enrolling hospice eligible patients while still hospitalized,¹⁴⁶ and flexibility in data collection to meet FCG preferences, we are confident in our ability to recruit the necessary 8 participants per month to meet the subject accrual goals in a timely manner.

Sample Size and Power Calculations

Determination of sample size is based on the analyses of study Aims 1 and 2 to detect a meaningful effect size. The focus of this study is FCGs. With a sample size of 100 FCGs per group, we will have 80% power to detect an effect size 0.487 at an alpha level of 0.01, assuming a two-sided, two-sample t-test is appropriate. This suggests that if a standard deviation of difference between two groups for a particular endpoint is 1 unit, then a difference of 0.487 points per month between two groups for that endpoint will be detectable with this sample size. Given that our primary outcome of interest is rate of change, only FCGs with at least one post-baseline measurement would be able to be evaluated. To account for a possible attrition rate of ~30%,⁹ due to unanticipated events such as loss to follow-up, we plan to recruit a total of 500 FCGs per group at an average of 8 FCGs per month over a planned 36-month enrollment period. We are confident we will enroll the target number of FCGs, as there were over 300 patients seen by the palliative care consulting service in both 2014 and in 2015 and discharged home to the major catchment area of the study setting.

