Aims 1 and 2. Statistical analyses of Aims 1 and 2 will be performed in a similar manner. Every FCG will be evaluated using various scales and survey instruments at baseline, 2 weeks, and 8 weeks post patient discharge (Table 1). We will use a response-feature analysis as our primary approach in analyzing these repeated measures data.¹⁸¹ For each FCG, the magnitude of the scores from the respective instruments will be plotted versus time (measured in months); least squares regression will be used to estimate a participant-specific rate of increase in points per month. This slope parameter estimate will be used as the response feature for each participant and is the primary endpoint for this study. The primary analysis of this endpoint will be analyzed using a two-sample t-test or Wilcoxon rank-sum test, as appropriate. The endpoints will also be analyzed using a fixed-effects linear regression model. This model will use the estimated regression-slope response-feature as the dependent variable and have independent variables consisting of intervention (yes, no) as well as any baseline covariates such as FCGs’ age, employment status, etc. These analyses will adjust for any possible imbalances in these baseline covariates among FCGs that occur due to the randomized assignment to the intervention. This analysis approach will hold for those endpoints collected only at two time points (i.e., baseline and 8 weeks).

Aim 3. Descriptive statistics, including mean, median, and standard deviation (minimum and maximum) for the utilization measures (i.e., hospitalizations and ED visits) will be provided. Considering the count nature of the utilizations, and to also account for any potential differences between the baseline characteristics of the care recipients in the two study arms, we will use Poisson regression to model various utilization outcomes.¹⁸² We expect that the gains (decreased healthcare utilization and costs) will be sustained beyond the enrollment period. Therefore, both descriptive and multivariable-adjusted measures will be estimated for the intervention period and the subsequent months post-intervention. A limitation of this economic approach will be the memory recall of the FCGs. We will provide a worksheet similar to Table 2 for all participants to help them track services and costs.

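### The primary slope test weights a baseline/week-2-only slope the same as a complete one and leaves the baseline score unadjusted: an efficiency cost, with an unidentified power SD and a recruitment figure that contradicts itself

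*Combined protocol and SAP*

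**What the plan says.** In the combined protocol and SAP, Analytical Plan, Aims 1 and 2, scores at baseline, 2 weeks and 8 weeks are reduced to one slope per caregiver: "least squares regression will be used to estimate a participant-specific rate of increase in points per month". That slope is the primary endpoint. "The primary analysis of this endpoint will be analyzed using a two-sample t-test or Wilcoxon rank-sum test, as appropriate". No weighting by number or spacing of visits is described. A secondary regression of the slopes has "independent variables consisting of intervention (yes, no) as well as any baseline covariates such as" age and employment status; the baseline score is neither named nor excluded.

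The only provision for two-point series is "This analysis approach will hold for those endpoints collected only at two time points (i.e., baseline and 8 weeks". Nothing is said about a series with baseline and week 2 only.

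Sample Size and Power Calculations says that "only FCGs with at least one post-baseline measurement would be able to be evaluated". It gives 80% power with 100 per group, two-sided alpha 0.01 and effect size 0.487, explained as "if a standard deviation of difference between two groups for a particular endpoint is 1 unit, then a difference of 0.487 points per month". It allows about 30% attrition and plans "a total of 500 FCGs per group at an average of 8 FCGs per month over a planned 36-month enrollment period".

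The Variables section places the baseline interview before discharge. Enrollment is looser: before discharge the coordinator is to obtain consent "and, if possible, collect baseline data".

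**The concern.** The precision of a least-squares slope depends on how far apart its time points are. A slope over two weeks is much noisier than one over eight, yet the primary test treats them alike, and a few noisy slopes can supply much of the variance. Such slopes are foreseeable: the plan names post-discharge data collection as a main challenge and accepts that collection after a care recipient's death may be difficult. The attrition allowance covers caregivers lost from the analysis, not those who remain with a poor slope.

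The baseline score also enters every slope, so chance variation in it feeds directly into the endpoint. The primary test makes no adjustment for it.

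At stake is power at 100 evaluable per group. The point covers outcomes measured at baseline and at least once later, so not Positive Aspects of Care, which is collected only at 6 months.

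**Working it through.** **1. The plan's own figure.** With 100 per group, d = 0.487 and two-sided alpha 0.01, the noncentral t gives 79.9%. The stated 80% reproduces.

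**2. Error variance of a slope.** With constant correlation between visits it is proportional to 1/Sxx, where Sxx is the sum of squared deviations of the visit times (weeks after discharge).

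| Baseline | Sxx, complete | Sxx, baseline and week 2 | Ratio |
|---|---|---|---|
| Discharge day | 34.67 | 2.00 | 17.3 |
| 1 week earlier | 42.00 | 4.50 | 9.3 |
| 2 weeks earlier | 50.67 | 8.00 | 6.3 |

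If correlation instead decays exponentially to between 0.3 and 0.7 at 8 weeks (assumed), the ratios for the same three rows are 5.8–4.5, 4.4–3.4 and 3.6–2.8. A baseline/week-8 slope loses almost nothing: 34.67/32 = 1.08 with constant correlation and 0.98 with decay. So the one two-point case the plan covers is the harmless one.

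**3. From error variance to total variance.** Power depends on total slope variance. If a share h of complete-slope variance is true difference between caregivers, the total ratio is T = h + (1 − h)R, where R is the error ratio. With h = 0.5, R = 17.3, 5.0 and 2.8 become T = 9.2, 3.0 and 1.9. As h approaches 1, T approaches 1. The documents give no value for h.

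**4. Power if 0.487 rests on the complete-slope SD.** With a share f of week-2-only slopes, the SD is multiplied by √((1 − f) + Tf). Take f = 0.10 (assumed), 100 evaluable per group, and an effect linear in time:

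| T | SD factor | Effective d | t-test power |
|---|---|---|---|
| 17.3 | 1.623 | 0.300 | 32% |
| 9.2 | 1.348 | 0.361 | 48% |
| 5.0 | 1.183 | 0.412 | 62% |
| 3.0 | 1.095 | 0.445 | 71% |
| 1.9 | 1.044 | 0.466 | 76% |

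At smaller shares (2% and 5%) power is 65% and 48% for T = 17.3, and 76% and 71% for T = 5.0. If the SD already describes the mix analysed, power stays near 80% throughout.

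**5. Keep or drop these slopes?** The equal-weight t-test does worse with them than without them when ((1 − f) + Tf)(1 − f) > 1, that is, when T > (2 − f)/(1 − f). The threshold is 2.05 at f = 5%, 2.11 at 10% and 2.8 at 45%. At f = 10%, dropping them leaves 90 per group and 75% power. Keeping them gives 71% at T = 3.0 but 76% at T = 1.9.

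**6. Baseline adjustment.** For complete data at 0, 14 and 56 days the monthly slope weights are −0.418, −0.167 and 0.585. With unit variances and constant correlation 0.5 (assumed), the slope variance is 0.5 × 0.545 = 0.272 and its covariance with baseline is 0.5 × (−0.418) = −0.209. Then r² = 0.209²/0.272 = 0.16, d becomes 0.487/√0.84 = 0.531, and power rises from 80% to about 88%. With decay to 0.5 at 8 weeks it is about 91%.

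**7. Simulated comparison.** 100 per group, 10 per arm with week-2 data only at random, linear effect, correlation 0.5 (constant, or decaying to 0.5 at 8 weeks), no further slope heterogeneity:

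| Analysis | Power, constant | Power, decay |
|---|---|---|
| Slope t-test | 34% | 63% |
| Slope Wilcoxon | 62% | 68% |
| t-test without two-point slopes | 75% | 75% |
| Mixed model, separate baseline means | 74% | 76% |
| Mixed model, common baseline mean | 83% | 88% |

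Null rejection at the nominal 1% was 0.9% and 1.2% for the t-test, and 1.1% and 1.1% for the Wilcoxon test. It was 0.8% and 1.0% for a mixed model with random intercept and slope, 1.1% and 1.1% with unstructured covariance, and 0.9% and 2.7% with a random intercept only.

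**8. Recruitment.** 8 × 36 = 288 in total, or 144 per group; 144 × 0.7 = 100.8 evaluable per group. The stated 500 per group gives 500 × 0.7 = 350 evaluable, with power 91.7% even at T = 17.3 and f = 10%.

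**The case against.** The strongest reply is that no shortfall is shown. The plan's SD is for the endpoint, and the evaluability rule follows directly, so the SD may well be that of the slopes as analysed; power is then near 80%. The share of week-2-only slopes is not in the documents. Repeated contact attempts, and collection about two weeks after a death, will reduce it: after a death on day 28, a slope from baseline and day 42 has an error ratio of only 1.9 (constant correlation) or 1.4 (decay). All of this stands, and the figures in step 4 are therefore conditional.

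A reader might put the 17.3 straight into the power formula, or conclude that these slopes always do harm. Neither is supported. The 17.3 concerns error variance, and harm needs a total ratio above about 2 together with a linear effect. Figure 2 sets at least two virtual visits a week in weeks 1–4 and one in weeks 5–8, so an early effect is plausible. If half the 8-week effect is present by week 2, the two-point slope shows 2.2 times the complete slope's difference. At 10% and a ratio of 2.8, keeping these slopes then gives about 82% against 75% for dropping them.

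It is also fair that a response-feature analysis is prespecified and valid, and that the Wilcoxon option limits the loss at high ratios. The mixed model's advantage comes mainly from the common baseline mean: with separate means it does no better than dropping the two-point slopes. That supports baseline adjustment as the main remedy. Finally, 350 evaluable per group would remove the shortfall at the 10% share, but 500 per group cannot be relied on while the same sentence implies 144.

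**Conclusion.** The concern holds as a matter of efficiency and of incomplete specification. The primary test gives equal weight to slopes whose error variances differ by a factor of about 3 to 17, has no rule for the imprecise ones, and does not adjust for the baseline score. If 0.487 rests on complete slopes, t-test power is about 32% to 76% at a 10% share with 100 evaluable per group, depending on the total-variance ratio (17.3 down to 1.9); otherwise it is about 80%. The share, the correlation and the slope heterogeneity are all assumptions.

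Two stronger inferences fail. The documents do not show that the 80% is wrong: it reproduces, and they do not identify the SD. Nor is the test invalid: with missingness random and equal between arms, its error rate stays near 1%.

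The recruitment contradiction needs no assumption. 500 per group cannot come from 8 per month over 36 months, whereas 288 in total matches the 100 evaluable per group in the power statement.

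**What to change.** 1. Adjust for the baseline score, which is already collected. The smaller change is to name it as a covariate in the slope regression. The fuller change is to make the primary analysis a prespecified likelihood-based mixed model on the raw scores. It would use actual assessment dates, a common baseline mean, a random intercept and slope, and arm-by-time as the test, which keeps points per month as the estimand. Name unstructured covariance as the fallback, not a random intercept alone. Keep the slope t-test/Wilcoxon as a sensitivity analysis.
2. Do not present weights by sum of squared time deviations as optimal. They are so only with constant correlation and no slope heterogeneity; at a total ratio of 1.4 and a 10% share they give about 75% power against 78% for equal weights.
3. In Sample Size and Power Calculations, state which slope SD the 0.487 refers to, and tie the 80% to 100 evaluable per group.
4. Correct the recruitment figure so that target, monthly rate and enrolment period agree.

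This changes wording only and needs no new data. The mixed model brings missing-at-random and covariance assumptions, and a wrong covariance can inflate type I error, so the model and its fallback should be fixed before outcomes are compared by arm.

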Aim 3: To examine the effect of technology-enhanced TPC for FCGs on healthcare costs. Recognizing the synergy between FCGs and care recipients, we hypothesize that costs from all stakeholders (FCGs, care recipients, and health systems) of providing palliative care to care recipients in the intervention group will decrease compared to usual care. Using the Ambulatory and Home Care Record (AHCRR), which is rooted in the societal perspective,^{1,25} we will measure all costs of care for the FCG and care recipient, irrespective of payer.^{26,27} We hypothesize that there will be a net decrease in costs for 6 months post-enrollment from a societal perspective following

the addition of a TPC for FCG in the intervention group compared to the costs of care for the FCG and care recipient in the usual care group.

This revised application is responsive to **FOA PAR-16-250**: examining an innovative model of TPC for FCGs in underserved rural areas to address the public health imperative based on the rapid growth in the need for palliative care services.²⁸ Our study is designed to extend transitional and palliative care science to contribute to the 2016 strategic plan priority of the National Institute of Nursing Research of exploring novel approaches for effective interventions to provide compassionate support to FCGs of patients with life-limiting illnesses.

RESEARCH STRATEGY

A. SIGNIFICANCE

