Another innovation of this application is the comprehensive assessment of the true financial burden borne by FCGs – a topic that has been recognized as a critical gap in the literature.¹ We will measure utilization and costs associated with TPC from a societal perspective, which will capture costs borne by the FCG, patient, employer, and health system irrespective of payers.^{1,25} Therefore, our study will help define the value, types, and sources of resources used in providing palliative care, including the out-of-pocket costs for medications, supplies, care providers, travel expenses, and forgone time (time costs) for FCGs.^{1,25,116}

Potential Impact

Rural America comprises over 97% of the total US land mass and contains approximately a quarter of the total US population.¹¹⁷ The findings from our proposed study will advance TPC strategies for FCGs of rural palliative care patients, and provide evidence of an effective care model to support continuity of in-home care for the FCGs of patients with life-limiting conditions. It is expected that providing TPC for FCGs of palliative care patients in underserved, rural areas will result in similar outcomes that already exist with TPC approaches in urban areas, including increased patient satisfaction, improved health outcomes, and lower healthcare costs. Further, the proposed study addresses three independent yet inter-related healthcare foci: transitional care, the needs of rural FCGs, and the rapidly growing field of palliative care. Our study will not only address the critical barrier imposed by distance, but also **extend palliative care practice** by

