A study nurse will develop an individualized FCG plan of care based on their assessment of FCG risks, needs, strengths, and preferences.¹⁵⁰ A unique plan of care to support FCGs includes: (1) a wellness plan to meet their own self-care (preventive and health-related physical and emotional wellness needs) and concerns during the transition period and (2) help for the FCG to meet the care recipient's needs. FCG Readiness Plans are key components of the FCG plan of care providing anticipatory guidance to address self-care needs and to meet common symptom management challenges for use by FCGs. The nurse will assist the FCG in implementing the plan of care and refine the plan of care to accommodate changing caregiving needs throughout the 8-week intervention through FCG advocacy, teaching, guidance, and counseling through in-person visits (during the hospital stay), and video visits and phone contacts at home. A copy of the individualized self-care plan will be provided to the FCG at the end of the intervention. [name] (Co-I) contributes the necessary expertise to oversee and train the study nurses in the TPC for FCGs intervention.

The TPC for FCG intervention will be provided by experienced, certified palliative care registered nurses. Review and recommendations of plans of care will be provided weekly and more often as needed by a study palliative care team (physician, pharmacist and social worker). Team meetings will focus collectively on identifying and meeting the unique caregiving and self-care needs of each FCG incorporating tenets of both transitional care and palliative care (Figure 2). Review and updates of the plans of care will be conducted with the FCG and other clinicians on the study team to meet mutually agreed and attainable goals.

Part 1: Pre-discharge intervention. The study nurse will make the first pre-discharge I visit with the FCG within 24 hours of study enrollment either in person or via video and every other day visits with the FCG during the remainder of the care recipient's hospital stay. The study nurse will have

Figure 2. Technology-Enhanced Transitional Palliative Care for Family Caregivers
Intervention Objectives

Caregiving in Palliative Care ^{103,108}	Caregiving in Transitional Care ^{18,143,149}	

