Aim 3: Examine the effect of technology-enhanced TPC for FCGs on healthcare costs. The Ambulatory and Home Care Record (AHCR) will be used as our healthcare cost measure. The AHCR is designed to capture costs from a societal perspective, implying that costs from all stakeholders (FCG, care recipients, and health systems) will be collected. Developed for the Canadian health system where healthcare is primarily publicly funded,¹ the AHCR will be modified for our study to collect expenditures paid for by any type of payer (e.g., commercial, government, or other insurance; and self-pay/no insurance) instead of simply publicly-financed expenditures as in the original AHCR. Third party insurance refers to any supplemental insurance over and above the primary insurance that the patient has (see Table 2). Thus, the proposed change to the original AHCR measure is only to increase clarity regarding funders and therefore we do not anticipate any threat to the AHCR's validity. The AHCR captures self-reported utilization and cost information for care provided by all FCGs and other unpaid caregivers, paid care received at home (e.g., home health care) and outside of the home (e.g., doctor/therapy appointments), as well as medications, supplies, and equipment. Out-of-pocket costs refer to all care-related expenses not paid for by the insurance. These data will be collected monthly for 6 months following each care recipient's discharge from the index hospitalization to minimize recall bias and to account for any time lag in billing systems. The FCGs will be prompted to have all bills received during the preceding month available during the monthly AHCR data collection. Agreement between care recipients' reports on the AHCR and administrative data range from moderate ($\kappa=0.41$; 95 percent confidence interval, 0.16–0.61) for physician visits to perfect ($\kappa=1.0$) for physical therapy visits.²⁵

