We will report these measures, per subject, every month to minimize the impact of patients dying in the earlier part of the intervention interval. The difference in costs of readmissions and ED visits between the intervention and control patients will provide an estimate of the costs avoided due to the proposed intervention. We anticipate that some care recipients will die before 6 months and therefore we will need to address right censoring of utilization and costs due to patients dying before the end of the study. Accordingly, we will adopt appropriate econometric methods as described in the **Analytical Plan section below** to account for the possible censoring of utilizations and costs.

The time costs refer to the FCGs' time and, if the FCG is employed, the employer time lost in the course of

Table 2: Modified Framework for Assessment of Palliative Care Costs¹		
Expenditure Category	Privately-incurred Costs	Time Costs
Third party-incurred Costs (Commercial/ Medicare/ Medicaid/ Other/ No Insurance)		
3rd Party Insurance Reimbursement (Yes/No)	Out-of-Pocket	Caregiver lost time from
• Home-based services	• Home-based services	• Labor Market
• Ambulatory appointments	• Ambulatory appointments	• Household work
• Hospitalization	• Hospitalization	• Leisure
• Emergency Department Visits	• Emergency Department Visits	
• Facility care	• Facility care	
• Medications	• Medications	Employer Time Loss
• Supplies and Equipment	• Supplies and Equipment	
	• Paid house work	
	• Travel expenses	
Total 3rd party Expenditures	Total Out-of-Pocket Expenditures	Total Time Cost

providing care to the care recipient. Time costs for the FCGs will be valued by a human capital approach.¹⁸⁰ The most recently available data on current earnings by age and sex from the Bureau of Labor Statistics (BLS) will be used to impute the market value of time withdrawn from leisure and household work. In order to value lost time from the labor market, age- and sex-based earnings from the BLS will be adjusted for employer-paid benefits, vacations days and holidays.

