For analyses of costs, standard descriptive statistics including mean, median, standard deviation, minimum and maximum will be provided for all cost outcomes measured individually and also for the overall cost measure. The difference in overall cost between the intervention and control group will provide an estimate of the cost impact of the TPC for FCG model of care. The difference in hospitalization and ED costs between the treatment and control arms will determine the cost avoidance potential of implementing the intervention. The difference in FCG cost, a component of the overall costs, between intervention and control groups will provide evidence on the impact of the intervention on this specific cost component. Both the descriptive and multivariable-adjusted measures will be estimated for 8 weeks and 6 months. Because the distribution of healthcare costs and length of stay (LOS) are generally skewed, both the LOS and costs will be log-transformed before any estimation; the estimated coefficients can then be interpreted as the approximate percentage changes. Alternatively, we will also explore modeling costs and LOS with a generalized linear model with gamma distribution and log link.¹⁸³ Furthermore, to account for the possibility that some of the study patients will die before the six-month follow-up; we will also apply econometric methods of censored regression.^{184,185}

Data Management

Following the data safety monitoring plan (see Protection of Human Subjects), the PI and investigative team will review the data to ensure quality, adherence to study procedures, and safety at monthly study team meetings. All participant data will be coded and stored in a secure, locked cabinet in the study coordinator's office. All data will be entered into the web-based Research Electronic Data Capture (RED-Cap) database and maintained on secure, password-protected servers, accessible only to members of the study team. The database will be exported to the statistical analysis package, SAS, to be analyzed anonymously, and standard Mayo Clinic policies and safeguards will be used to protect the confidentiality of the subject records.

Expected Outcomes

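### Aim 3 claims a net societal saving, but the cost measurement has no source or line for the study-funded cost of delivering the intervention, so the overall cost difference as planned leans towards a saving

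*Combined protocol and SAP*

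**What the plan says.** The Specific Aims (Aim 3) hypothesize that "there will be a net decrease in costs for 6 months post-enrollment from a societal perspective" once the programme is added. The scope is broad. The Innovation section promises to measure "costs associated with TPC from a societal perspective, which will capture costs borne by the FCG, patient, employer, and health system", and the Aim 3 part of Variables and Their Measurements says that "costs from all stakeholders (FCG, care recipients, and health systems) will be collected".

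The measurement is narrower. The only cost instrument named is the Ambulatory and Home Care Record (AHCR), a monthly self-report: "The FCGs will be prompted to have all bills received during the preceding month available during the monthly AHCR data collection". Costs are laid out in Table 2, "Modified Framework for Assessment of Palliative Care Costs", which has three totals: third-party, out-of-pocket and time. Time is valued for the caregiver (FCG) and the employer only. The Analytical Plan adds: "We will provide a worksheet similar to Table 2 for all participants to help them track services and costs".

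The estimate is then defined: "The difference in overall cost between the intervention and control group will provide an estimate of the cost impact of the TPC". It is to be given at 8 weeks and 6 months. Costs and length of stay (LOS) are put on the log scale ahead of estimation. A gamma model with log link is to be explored as an alternative. Censored regression is added because the plan treats death as right-censoring.

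On the intervention side, palliative care nurses make hospital and video contacts, and "Review and recommendations of plans of care will be provided weekly and more often as needed by a study palliative care team". An iPad is supplied to FCGs who choose one, and technical support is available around the clock. Contacts are logged, but the stated purpose is to quantify dose. Control FCGs get a reminder call.

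**The concern.** A net saving is what remains after paying for the programme. The plan itself separates two quantities: hospitalization and emergency department (ED) differences give avoided cost, and the overall difference gives cost impact. The second is a net figure only if delivery is counted, and no step counts it.

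The omission favours the hypothesis. A cost-neutral or cost-raising programme could be reported as saving money. The Potential Impact section says that knowing the cost impact will be crucial for scaling up, so a health system could be deciding without the price of what it would buy.

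Two smaller matters affect the same estimate. The log of a zero cost is undefined, and log-scale coefficients are percentage changes, not the dollars that a net-saving claim needs. Also, a care recipient's own healthcare cost after death is known to be zero; it is not unobserved.

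**Working it through.** **1. Trace each delivery resource to a cost line.**

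| Resource | Where described | Source or line in the AHCR / Table 2 |
|---|---|---|
| Nurse contacts | Experimental Group; Figure 2; Parts 1 and 2 | No charge to a payer or FCG is described, so nothing to value |
| Weekly physician, pharmacist and social worker review | Experimental Group | None; the FCG does not see this time |
| Study iPad, technical support | Part 2 | Paid by the study; no charge described |
| Reminder calls (control arm) | Control group | None, but small |

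The Aim 3 hypothesis runs from enrollment, while the AHCR runs from discharge, so hospital-stay contacts also precede the collection window.

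**2. Direction.** Let D be the delivery cost per intervention FCG and c the cost of control calls per control FCG. In arithmetic means:

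reported difference = true net difference − (D − c)

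D exceeds c, so the shift is towards a saving. On the log scale it appears as a ratio. If every FCG had true cost Y, the ratio would be (Y − D)/Y, ignoring c, which is below 1 and so in the same direction.

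**3. Size: illustration only.** The plan states no delivery cost, unit cost or cost difference, so there is no figure of its own to reproduce for this point. (Its only Aim 3 power figures, 87% for hospitalizations and 75% for ED visits, concern utilization. A two-sample t-test gives 75.1% and 88.6%, as if the labels were exchanged. That is a separate matter and is not used here.)

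- From the documents: minimum home visits are 2 × 4 + 1 × 4 = 12 (Figure 2) or 1 × 8 = 8 (Part 2 text). Team review is 8 weeks × 3 disciplines.
- Assumed: 0.5 to 1.5 nurse-hours per visit at $50 to $100 per hour; 10 minutes per discipline per week at $75 to $150 per hour.
- Nurse time: 8 × 0.5 × $50 = $200, up to 12 × 1.5 × $100 = $1,800.
- Team review: 8 × 3 × 10 min = 4 h, so $300 to $600.
- D = $500 to $2,400, before hospital-stay visits, phone calls, equipment and technical support.

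For scale, the Sample Size section assumes healthcare cost of $2,000 per month (SD $1,000) with 100 per group. Six months is 6 × $2,000 = $12,000. If the true net difference is zero, the chance of a significant saving is Φ((D/6)/SE − z), with SE = 1,000 × √(2/100) = $141.4 per month, c ignored, and z = 1.960 (alpha 0.05, used in the Aim 3 power statement) or 2.576 (alpha 0.01, Analytical Plan).

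| Assumed D | D/6 per month | D/$12,000 | Chance at 0.05 (nominal 2.5%) | Chance at 0.01 (nominal 0.5%) |
|---|---|---|---|---|
| $500 | $83 | 4.2% | 8.5% | 2.3% |
| $1,000 | $167 | 8.3% | 21.7% | 8.1% |
| $2,000 | $333 | 16.7% | 65.4% | 41.3% |
| $2,400 | $400 | 20.0% | 80.7% | 60.0% |

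On the log scale, with everyone at $12,000, the omission alone gives ln(11,500/12,000) = −0.043 at $500 and ln(9,600/12,000) = −0.223 at $2,400.

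**4. Zeros.** An FCG whose care recipient has no readmission or ED visit contributes zero hospitalization cost, ED cost or readmission LOS. The plan gives no rule for these. The gamma distribution is also defined for positive values only, so the alternative as named does not settle the matter. Overall cost is little affected, because it is rarely zero.

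**The case against.** **Silence is not a decision to count nothing.** The declared perspective covers health-system costs and costs associated with the programme, and no text excludes delivery. This stands. A reader might infer that the investigators chose to leave delivery cost out, and the documents do not support that. What they show is a declared scope with no data source, unit cost or valuation step behind it.

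**Table 2 has lines for home-based services and for supplies and equipment.** An FCG might enter video visits there. But no text says that the visits are billed, and an entry with no insurer charge and no out-of-pocket payment is valued at zero. FCG time spent in visits may be counted as time cost, which is not delivery cost. The modified AHCR form (Appendix B) and the procedure manual are not in the text reviewed, and this limits confidence.

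**The plan does not rely on logs alone.** It also plans arithmetic means for each cost and for overall cost, and a gamma model of mean cost. This stands. The objection to percentage changes applies to the log-transformed model only; the remaining gap is that no estimate is named as the main one.

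**Death is already considered.** Monthly per-subject reporting is planned to limit the effect of early deaths, the censored regression is an added analysis, and some data after death may truly be missing because bills lag or the FCG cannot be reached. All of this stands, and since no estimator is named, no size is claimed.

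**Aim 3 is not primary.** The sample size rests on Aims 1 and 2, and the primary endpoint is the slope. This limits the severity but does not remove the bias from the Aim 3 headline.

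**Conclusion.** The point holds and should be fixed; confidence is medium. If the plan is followed as written, the overall cost difference is biased towards the hypothesized saving. In arithmetic means the shift is the delivery cost per FCG less the cost of control calls. On the log scale it is a ratio in the same direction.

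The direction follows from the accounting. The size does not: every dollar figure for D is an assumption. The false-saving chances also assume 100 analysed per group and an SD of $1,000 for each FCG's six-month average monthly cost, and they borrow a healthcare cost that is not the overall societal cost.

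Three stronger readings are tempting but unsupported:
- That the 8-week estimate is the more biased. Per month the shift is larger there only because the same cost is divided by a shorter window; as a window total, home-delivery cost adds the same dollars at both times.
- That the power section's mean counts reveal how many participants have zero cost. Whole-number counts with means 0.75 and 0.45 need SDs of at least √(0.75 × 0.25) = 0.433 and √(0.45 × 0.55) = 0.497. The plan states 0.4 and 0.2, so the figures cannot be read as whole counts per person over the window.
- That any reported saving would be false. A true saving larger than D − c would survive the correction.

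**What to change.** 1. **Cost the delivery.** Add to the Analytical Plan a provider-side component, separate from the FCG worksheet. Value it from the contact log (including hospital-stay contacts), team-review time, equipment and technical support. Cost control calls in the same way. Exclude research-only items such as fidelity audits and participant remuneration. Include it in overall cost at 8 weeks and 6 months, and report the difference with and without it. For consistent unit costs, these passages must be reconciled: home-visit minimums (Figure 2 against Part 2), hospital-contact frequency (every other day in Part 1, daily in Figure 2) and nurse grade (registered nurse in the Experimental Group text, advanced practice nurse in Figure 2).
2. **Name the main estimate.** Use the arithmetic mean dollar difference in overall cost with a confidence interval, which the planned descriptive means already allow. Use a model that accepts zeros, for example a two-part model, for component costs and LOS. Keep the log model as a sensitivity analysis.
3. **Handle death explicitly.** In the added censored analysis, count the care recipient's own healthcare cost after death as zero. Reserve censoring for withdrawal, loss to follow-up or bills not yet received.

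The cost is a few sentences, modest costing work and a new record of team-review time; FCGs have nothing more to complete. The price is wider intervals on the dollar scale and a less favourable net saving.
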